Official Title: PET and MRI Brain Imaging of Bipolar Disorder

NCT: NCT01880957

Document Date: 11/14/2017

Proposed Statistical Plan for [11C]-DASB (5-HTT) & [11C]-CUMI-101 (5-HT1A) from [name] **Bipolar Study**

Outcomes

DASB: V_T/f_p + bootstrap ROI error

CUMI: BP_F + bootstrap ROI error (BP_{ND}??)

A priori ROIs

DASB: acn, amy, midbrain, gcirc

CUMI: acn, amy, cin, dlPFC, parahippocampal gyrus, hippocampus, raphe

Statistical methods:

Linear mixed models with subject fit as random variable LMM also with DASB & CUMI reference regions and fp

Key outcomes: p-values for main effects/interactions; overall model R² & p-value; standardized & unstandardized β's, 95% CIs, p-values for post-hocs

Covariates

DASB: age

CUMI: age, sex, previous med status (dichotomous – w/n 4 years)

Post-Treatment

Sample: HC, pre BPD, post BPD

Question 1: Do post-treatment BPD levels of DASB or CUMI differ from pre-treatment levels and HCs?

Interactions of interest:

Group (relationship btw brain & Group across all regions) **Group*ROI** (ROI-specific relationship btw brain & Group)

Treatment Effects

Sample: pre/post BPD pairs

Tx response: % change in HDRS-24 (continuous) and remitter/non-remitter (dichotomous)

Question 2: Is the % change in DASB or CUMI associated with the treatment outcome?

Interactions of interest:

AHDRS (relationship btw brain & Tx outcome across all regions) **ΔHDRS*ROI** (ROI-specific relationship btw brain & Tx outcome)

Dichotomous

Interactions of interest:

Remission (relationship btw brain & Tx outcome across all regions)

Predicting Treatment Outcome

Sample: pre BPD with pre HDRS-24 + >7-week HDRS-24

Tx response: % change in HDRS-24 (continuous) and remitter/non-remitter (dichotomous) (responder ??)

Question 3: Do pre DASB or CUMI in any of the *a prioris* predict treatment response? Are the *a prioris* independent predictors of treatment response?

Interactions of interest:

PET roi (pre-treatment PET in ROI predicts treatment response)

Interactions of interest:

PET_roi (any significant ROIs are independent predictors of Tx response (over and above the other ROIs))

Same models fit with dichotomous remission status

Additional question: Do pre DASB & CUMI together predict more of the variance in treatment response than either method alone?

Change in overall model R² from models with pre DASB & CUMI alone to combined model (If R² increases with both methods, tracers are predicting unique properties of Tx response)

Question 4: With what accuracy does pre DASB or CUMI predict treatment response?

Penalized logistic regression models

Additional question: With what accuracy do pre DASB & CUMI together predict treatment response Metrics of interest:

Accuracy, AUC, sensitivity, specificity, NPV, PPV, model factor importance ranking or % of variance explained with each factor

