To assess the impact of lithium on the neuroreceptor measures we conservatively use the higher test/retest variability of the [¹¹C]DASB compound and assume a 20-25% change in both 5-HT_{1A} and 5-HTT after chronic lithium based on preclinical data. ¹4,16-18 Assuming 50% of the subjects complete the lithium treatment and repeat scans and this degree of change, we have a power of between 79% and 90% as this is a paired analysis. Estimated outcome measures will be analyzed for all ROIs and all patients in a linear mixed model with patient as random effect and ROI and remission status as fixed effects. Our previous studies have demonstrated that the standard deviation of BP across patients increases approximately linearly with the mean of the region, and so the BP values are first log-transformed in order to satisfy the assumptions of the modeling (constant variance across regions). For the pre/post imaging of the non-remitters, a linear mixed model will again be used with ROI and condition (before/after) as fixed effects and with two levels of random effects -- a patient effect and a study within patient effect. Many potential covariates will also be measured for each patient and will be included in the model when appropriate. Modeling will be done using R software (www.r-project.org).

F. Funding Status, Details

The study is currently funded through the National Institutes of Health (NIH) through May 31, 2017. Grant Title: Lithium's Molecular Mechanism of Action and the Pathology of Bipolar Disorder

G. Human Subjects Research Protection from Risk

1. Risk to Subjects and 2. Adequacy of Protection Against Risks

Risks associated with participation in this study are related to 1) Drug-free interval; 2) placement of intraarterial catheter; 3) blood sampling; 4) discomfort during scanning (PET and MRI); 5) MRI scan; 6) radiation exposure; 7) toxicology (idiosyncratic reaction to the tracer); 8) genetic testing/confidentiality; 9) pregnancy and 10) risks associated with lithium/lamotrigine use.

Stony Brook University Human Subjects Committee (IRB) PSF 2/23/15

Page 23 of 37

IRB# 2012-1826-F PI: [name] 1. Drug-free interval

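### SAP Question 1 names only a subject random term although patients are scanned twice, so the pre/post and overall Group tests use a wrong error term (direction unknown) and Group*ROI loses power

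*SAP*

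**What the plan says.** The SAP, under Statistical methods, gives one general statement on random effects: "Linear mixed models with subject fit as random variable". It names no scan or session term and no other covariance structure. Under Post-Treatment the data are "Sample: HC, pre BPD, post BPD", and the question is "Question 1: Do post-treatment BPD levels of DASB or CUMI differ from pre-treatment levels and HCs". Group and Group*ROI are the terms of interest. The a priori regions number 4 for DASB and 7 for CUMI.

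The protocol (section D.5, PET Studies) gives treated patients a second PET session and healthy volunteers none.

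Protocol section E, Power Analyses, describes two models. The first reads "Estimated outcome measures will be analyzed for all ROIs and all patients in a linear mixed model with patient as random effect", with ROI and remission status as fixed effects. The second is restricted in scope, "For the pre/post imaging of the non-remitters, a linear mixed model will again be used", and is fitted "with two levels of random effects -- a patient effect and a study within patient effect". The same section sizes the paired comparison "Assuming 50% of the subjects complete the lithium treatment and repeat scans".

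**The concern.** All regions in one scan share that scan's plasma free fraction and arterial input function, so an error in either moves them together. A patient with two scans therefore has two levels of clustering: values within a scan, and scans within the patient. The SAP names only the outer level. The protocol names the inner one, but for a subset of patients that is not the Question 1 sample.

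If the inner level is left out, the change from pre to post is judged against a pooled residual that does not measure how much a whole scan varies from one session to the next. The pre/post change is half of Question 1 and bears on Aims 2 to 4. Group*ROI carries the regional prediction in Protocol C.2, that lithium lowers cortical but not somatodendritic 5-HT1A binding. A reader of the planned p-values and 95% CIs could not tell whether a treatment change was exaggerated, hidden or about right.

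**Working it through.** **The plan's own figure.** The protocol states 79–90% power for a 20–25% paired change. It gives no SD of the difference, so this cannot be reproduced. Back-solving for 19 pairs (50% of 38), two-sided 5%: 79% power at a 20% change needs an SD of 0.298, which then gives 93% at 25%. The only retest figure (section G, Toxicology: CV under 10% for CUMI) is not split into a part shared by all regions and a part specific to each. Neither figure yields the variances needed here.

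**Expected mean squares.** Let R be the number of regions and take balanced pairs. The variances are s2_scan (shared by all regions of a scan), s2_subjROI (a patient's stable regional pattern) and s2_resid.
- Correct error for pre/post: s2_resid + R·s2_scan.
- Error used by the subject-only model: s2_resid + [R·s2_scan + 2(R−1)·s2_subjROI]/(2R−1).
- The two are equal when R·s2_scan = s2_subjROI. Above that the test is too liberal; below it, too conservative.
- For pre/post-by-ROI the correct error is s2_resid. The pooled error is never smaller, so that part of Group*ROI is conservative.

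**Worked case.** Assume s2_scan + s2_resid = 1 and write ρ = s2_scan, v = s2_subjROI. The layout is 38 controls, 38 pre and 19 post scans. The 57 single-scan subjects each give R−1 within-subject degrees of freedom with error s2_resid + v; the 19 pairs each give 2R−1. (Fixed-effect degrees of freedom are ignored.)
- R = 4, ρ = 0.5, v = 0: pairs 0.5 + 2/7 = 0.786; pooled (171×0.500 + 133×0.786)/304 = 0.625; correct 0.5 + 2 = 2.50. SE ratio √(0.625/2.50) = 0.50, so rejection is P(|Z| > 0.98) = 33%.
- R = 7, same ρ and v: pooled (342×0.500 + 247×0.769)/589 = 0.613 against 4.00; SE ratio 0.39; 44%.
- R = 4, ρ = 0.25, v = 1: pooled and correct errors are both 1.75; 5%.
- R = 4, ρ = 0.1, v = 3: pooled 3.74 against 1.30; SE ratio 1.70; 0.1%.

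**Simulation, same layout.** Null data, subject variance 2, 4,000 runs per cell, subject-only REML with Satterthwaite degrees of freedom, covariates left out. Rejection at nominal 5%, for ρ = 0.1 / 0.25 / 0.5:

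| Test | v = 0 | v = 1 | v = 3 |
|---|---|---|---|
| Pre/post, 4 ROIs | 10/18/33% | 2/5/12% | 0.3/0.4/2.5% |
| Pre/post, 7 ROIs | 13/28/46% | 3/10/21% | 0.2/2/7% |
| Group, 4 ROIs | 8/14/28% | 3/5/10% | 2/3/4% |
| Group, 7 ROIs | 10/23/40% | 4/8/16% | 2/3/6% |

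In these cells Group*ROI rejected 1.4–5.3%, pre versus control 4.1–5.7% and post versus control 3.5–7.2%. Post versus control rose to about 10% with subject variance 1, ρ = 0.5 and 19 pairs, and to 9–12% with 10 pairs. A separate set of runs gave 11–14% where scan variance equalled between-subject variance. With scan and subject-by-ROI terms added, all tests lay at 3.9–6.2%.

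Varying subject variance (1 or 4) or the number of pairs (10 or 38) left pre/post at 30–35% (4 ROIs) and 42–45% (7 ROIs) for ρ = 0.5, v = 0.

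**Group*ROI power.** ρ = 0.5; 2 of 4 or 3 of 7 regions change, by an amount that a correct analysis of 19 pairs detects with 80% power; v = 0 / 0.5 / 1:

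| Random terms | 4 ROIs | 7 ROIs |
|---|---|---|
| Subject only | 83/51/32% | 80/41/24% |
| Subject + scan | 92/59/35% | 92/51/29% |
| Subject + scan + subject-by-ROI | 92/82/78% | 92/80/76% |

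**A change hidden.** At ρ = 0.1, v = 3, a change common to all regions that the full model detects pre/post with about 80% power is found with 41% (4 ROIs) or 47% (7 ROIs) by subject-only.

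**The case against.** The strongest reply is that the SAP is a bulleted outline with open question marks. It writes no model formula and does not say that subject is the sole random term, so an analyst might add the scan level unprompted. That is fair as to intent. It does not remove the problem, because no other random term appears anywhere in the SAP and the protocol spells out a second level where it wants one.

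A reader might infer that the protocol deliberately omits the scan level for all patients. The text does not support that. The all-patients model lists no before/after factor and may hold one scan per patient, in which case one random level is right. What stands is narrower: the two-level structure is limited to non-remitters, and the SAP does not repeat it.

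A reader might also argue that Group*ROI keeps adequate power, since 83% and 80% at v = 0 meet the usual benchmark. The proper comparison is the 92% that a correct model reaches in the same layout. The severe losses do depend on subject-by-ROI variance, which neither document mentions. The regional prediction in Protocol C.2 concerns 5-HT1A, so the 7-ROI column is the relevant one.

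The SAP also lists a bootstrap ROI error and separate models of reference regions and free fraction. Neither supplies the missing covariance. With unequal ROI error variances, inverse-variance weighting left pre/post rejection unchanged at 32% (4 ROIs) and 43% (7 ROIs).

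**Conclusion.** The point holds: as written, the pre/post part of Question 1, and through it omnibus Group, rests on the wrong error term. It should be fixed before analysis.

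Two stronger readings are tempting. One is that the plan inflates false positives. The documents do not show this, because direction turns on whether R·s2_scan exceeds s2_subjROI and neither variance is given. If the protocol's patient-plus-scan structure is right and there is no subject-by-ROI variance, the test is too liberal; with substantial subject-by-ROI variance it can be too conservative or about right. The other is that every comparison with controls is safe, or that every one is compromised. Pre versus control is calibrated. Post versus control is near nominal in many settings, but reaches about 10–12% (14% at the extreme of the runs) when scan variance is large relative to subject variance or pairs are few.

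Group*ROI is conservative and loses power relative to the correct model: from 92% to 80–83% at ρ = 0.5 without subject-by-ROI variance, and from 76–78% to 24–32% at v = 1.

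Confidence is high on the missing term and the direction rule. The sizes rest on assumed variance components, 19 pairs and models without covariates.

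**What to change.** In the SAP, for every model that holds both pre and post scans, and for all bipolar patients, specify random intercepts for subject, scan within subject and subject-by-ROI, with Satterthwaite or Kenward-Roger degrees of freedom. Drop a term only if its variance is estimated at zero. Align the SAP with Protocol section E, widening the protocol's two-level structure beyond non-remitters, and state how the bootstrap ROI error enters the model.

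Both added terms are needed. The scan term repairs the false-positive risk. It leaves a conservative pre/post test as it was (0.3% and 0.2% at ρ = 0.1, v = 3) and does not restore the Group*ROI power lost to subject-by-ROI variance. A paired test on each patient's ROI-mean change is a simple sensitivity check for complete pairs.

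The cost is about one line of text and two model terms, with no extra data or patient burden. The pre/post p-value may become less favourable, and with few pairs a variance component may be estimated at zero.

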- 3. Assess the effect of lithium treatment of bipolar disorder on 5-H T_{IA} BP. Chronic lithium in animal studies does not affect somatodendritic 5-HT_{1A} B_{max} in the dorsal raphe nucleus but decreases 5-HT_{1A} B_{max} in frontal cortex and hippocampus. We propose to perform baseline 5-HT_{1A} scans with [11C]CUMI-101 or [18F]MeFWAY and repeat scans 6-10 weeks from the time of therapeutic or highest tolerable dose of lithium monotherapy. Our preliminary 5-HT_{1A} data in bipolar subjects suggest that as a group they have slightly higher 5-HT_{1A} BP than controls with a sex by diagnosis interaction. We hypothesize that regardless of sex, 5-HT_{1A} BP will downregulate in response to chronic lithium.
- 4. Assess the effect of lamotrigine treatment of bipolar disorder on 5-HTT and 5-HT₁₄ BP. We estimate based on our experience with bipolar subjects in our clinic that 50% of the subjects will not be eligible for lithium monotherapy. We propose to treat this group with lamotrigine. Lamotrigine, like lithium, alters 5-HT_{1A} B_{max} and also activity. There are no data regarding lamotrigine and its effects on 5-HTT. We propose to explore the effect of lamotrigine on 5-HTT and 5-HT_{1A} in order to determine if this medication also acts via alteration of these proteins. We will determine the relationship between BP change and antidepressant effect.
- 5. Assess the effect of lithium treatment of unipolar depression on 5-HTT BP. We will perform baseline and

Approved: 12/13/2019
Expiration Date: 12/12/2020
Stony Brook University Human Subjects Committee (IRB)
PSF 2/23/15

Page 2 of 37

IRB# 2012-1826-F PI: [name]

post treatment [11C]DASB scans in 10 unipolar depressed subjects. We will determine if the effects of lithium treatment are specific to bipolar depression.

B. Background and Significance

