Statistical analyses performed included Student's t-test, one way analysis of variance, and linear mixed models analysis with subject as the random effect. Model fitting was computed using both SPSS 11 for Mac OSX (www.spss.com) and R (www.R-project.org). When multiple regions were considered in a single

[figure not shown]

Figure 4: Trends for higher 5-HT_{1A} BP in male bipolar patients and lower 5-HT_{1A} BP in female bipolar patients.

analysis, region was included as a fixed effect, and the analysis was performed on the natural log of BP, in order to account for heterogeneity of variances across regions. Significance was defined as p < 0.05 and p-values are reported without multiple comparison adjustment. tests were two-sided. In all models, there were no interactions, first or higher order, therefore, the interaction terms were not included in the models. Data are presented as mean \pm standard deviation.

There was no difference in percentage of females between controls (56%) and bipolar subjects (60). They also did not differ in age (controls = 37.3 ± 14.5 , BPD = 39.04 ± 10.0 , p = 0.640). The control population presented here is the same as in our previous publication.²²

Across all regions there was slightly higher BP in BPD subjects scanned during a MDE compared to controls but this did not reach statistical significance (F = 0.592; df = 1, 54; p = 0.444; Figure 3). We have previously reported that females have significantly higher 5-HT_{1A} BP than men and that there is a correlation between lifetime aggression scores and BP. 153 As this is preliminary data, we do not have lifetime aggression scores for all the subjects but when we include gender in the linear mixed effects model we get a significant gender by diagnosis interaction (F = 5.99; df = 1, 54; p = 0.018). In contrast to the our findings in unipolar depression, it appears that male bipolar subjects

Stony Brook University Human Subjects Committee (IRB) PSF 2/23/15

Page 8 of 37

IRB# 2012-1826-F PI: [name]

have higher 5-HT_{1A} BP compared to male controls while female bipolar patients have lower BP compared to female controls (Figure 4). We have also shown that prior medication status has a major effect on 5-HT_{1A} BP²² however 90% of the bipolar subjects had been previously exposed to medication.

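### CUMI Question 1 pre-specifies no Group*sex term, although the protocol's preliminary 5-HT1A data suggest a diagnosis effect that differs by sex, which would dilute the pooled patient-versus-control contrasts

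*SAP*

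**What the plan says.** The SAP's Covariates section gives "CUMI: age, sex, previous med status (dichotomous – w/n 4 years") for this tracer. Sex is in the model, but only additively.

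Under Post-Treatment, the sample is "Sample: HC, pre BPD, post BPD", and Question 1 compares post-treatment patients with their pre-treatment levels and with healthy controls. The listed terms are "Group (relationship btw brain & Group across all regions") and Group*ROI, glossed as "ROI-specific relationship btw brain & Group". No sex interaction is named anywhere in the SAP. Its Statistical methods section asks for p-values for main effects and interactions, without saying which interactions.

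Protocol section C.2 reports no overall 5-HT1A difference between bipolar subjects and controls (F = 0.592; df = 1, 54; p = 0.444). Once gender is added, it reports a "significant gender by diagnosis interaction (F = 5.99; df = 1, 54; p = 0.018"), with bipolar men above male controls and bipolar women below female controls. Aim 3 restates this, describing bipolar subjects as slightly higher "than controls with a sex by diagnosis interaction". The end of section C.2 expects lithium to bring men to control level and possibly take women below it. Aim 3 hypothesises that lithium lowers binding in both sexes.

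**The concern.** The protocol's one significant preliminary 5-HT1A diagnosis finding is an interaction, and the SAP's CUMI model has no term for it. One Group effect with sex as an additive covariate estimates a single patient-versus-control difference averaged over men and women. If the two differ in sign, the average is smaller than the larger of them, and the test can miss a difference that is present in one sex. A null Group result could then be reported as no 5-HT1A abnormality in bipolar depression.

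The same applies after treatment. The protocol's expected post-lithium positions relative to controls differ by sex, and a pooled contrast cannot display them. If Group*sex is first examined after the data are seen, it counts as exploratory, although the protocol had already raised it.

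**Working it through.** **Inputs.**
- Protocol C.2: 20 bipolar subjects (60% female) and 41 controls (56% female), taken here as 12 women and 8 men, and 23 women and 18 men. These counts come from rounded percentages and are an assumption. The reported error df of 54 does not obviously match 61 subjects.
- Interaction F = 5.99 and pooled diagnosis F = 0.592, both on 1, 54 df.
- Protocol D.3 and E: 38 bipolar and 38 controls, sexes about equal, and half assumed to complete lithium and repeat scans.
- Two-sided alpha of 0.05, as in C.2. The SAP states none.

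**Reproducing the protocol's figures.** F(1,54) = 5.99 gives p = 0.0177 (stated 0.018). F(1,54) = 0.592 gives p = 0.445 (stated 0.444; rounding of F).

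**Implied effects in SD units** (subject-level approximation, equal variances), using d = √F × √(sum of 1/n):
- Interaction: √5.99 × √(1/12 + 1/8 + 1/23 + 1/18) = 2.447 × 0.554 = 1.36 SD.
- Pooled: √0.592 × √(1/20 + 1/41) = 0.769 × 0.273 = 0.21 SD.
- Precision weights: women 1/(1/23 + 1/12) = 7.89, men 1/(1/18 + 1/8) = 5.54. The women's share is 7.89/13.42 = 0.587.
- Women: 0.21 − 0.413 × 1.36 = −0.35 SD. Men: 0.21 + 0.587 × 1.36 = +1.01 SD.
- Sex-specific tests on these figures: men t = 1.01 × √5.54 = 2.37, p about 0.02; women t = −0.35 × √7.89 = −0.98, p about 0.33.

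**Pooled Group contrast, 38 versus 38** (SE = √(2/38) = 0.229).
- Equal sexes: average (1.01 − 0.35)/2 = 0.33 SD; 0.328/0.229 = 1.43; power 29–30%.
- Preliminary pooled effect carried over unchanged: 0.21 SD; 0.21/0.229 = 0.91; power 15%.

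**Group*sex for pre-treatment patients versus controls, 19 per cell** (SE = √(4/19) = 0.459; noncentral t, 72 df).

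| True interaction | Ratio to SE | Power |
|---|---|---|
| 1.36 SD (full) | 2.96 | 83% |
| three quarters | 2.22 | 59% |
| half | 1.48 | 31% |

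**Group*sex for 19 post-treatment patients versus 38 controls.** SE = √(2/19 + 2/9.5) = 0.562; 1.357/0.562 = 2.41; power about 66% at the full interaction.

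**Time*sex in about 19 pre/post pairs.** Protocol section E gives 79–90% power for the paired change. With 19 pairs this implies a mean change of about 0.67 to 0.79 SD of the change scores. Suppose the sexes differ by as much as that whole average effect. With 9.5 per sex, SE = √(2/9.5) = 0.459, the ratio is 1.46 to 1.71, and power is only about 28–37%.

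**The case against.** The evidence for the interaction is thin. It is one p-value without multiplicity adjustment, from about 8 bipolar men. The tracer was [11C]WAY-100635, not CUMI-101, and the Figure 4 caption calls the sex-specific differences trends. Section C.2 also states that no model contained interactions, shortly before reporting "gender by diagnosis interaction (F = 5.99; df = 1, 54; p = 0.018"). A reader might infer that opposite effects in men and women are established and that the Group test will come out near zero. The documents do not support that: by the approximation above only the male difference is nominally significant, and the average at equal sexes is 0.33 SD.

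A reader might also infer that all of Question 1 is compromised. It is not. The pre/post comparison is within patients, and Aim 3 predicts the same direction of change in both sexes, so a sex by diagnosis interaction does not dilute it.

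The 83% is a favourable case. It takes a selected preliminary estimate at face value and assumes that all 38 per group have CUMI scans. The protocol allows participants to have only one tracer, and lets patients, but not controls, be scanned with [18F]MeFWAY instead.

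Finally, the SAP is an outline, its reporting line mentions interactions generically, and protocol section E allows covariates when appropriate. An analyst could therefore fit Group*sex. That is true, but neither line pre-specifies it. The weakness of the preliminary evidence is a reason to state the test in advance as secondary, so that it can be confirmed or refuted.

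**Conclusion.** The point holds for the CUMI healthy-control-versus-bipolar contrasts, before and after treatment. If the preliminary pattern is real, the pooled test at 38 versus 38 has about 30% power at an equal sex mix, or 15% if the preliminary pooled effect is carried over. Group*sex has about 83%, falling to 59% and 31% at three quarters and half of the preliminary interaction. With 19 post-treatment patients it is about 66% at full size, provided that the sex by diagnosis difference persists after treatment.

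These figures rest on cell counts inferred from percentages, equal variances, a subject-level approximation to the mixed model, and the carry-over of a WAY-100635 result to CUMI-101. The 38-versus-38 figures also need complete CUMI scanning. They show how much could be missed and do not predict a null result. The plan remains usable without the term, but adding it is a cheap and worthwhile improvement.

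**What to change.** - Pre-specify Group*sex as a secondary term in the CUMI Question 1 model for the healthy-control-versus-bipolar contrasts. Report the group contrasts separately for men and women with 95% CIs.
- State that a null pooled Group result will not be reported as no 5-HT1A abnormality without those sex-specific estimates.
- Report time*sex in the pre/post CUMI model only as a descriptive estimate with a 95% CI. About 19 completers cannot confirm that lithium acts alike in both sexes.
- Reconcile the statement in protocol section C.2 that no interactions were found with the significant interaction reported after it.

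The cost is one or two degrees of freedom, since Group has three levels, and one more reported test. Sex is already recorded and already in the model, so no new data are needed.

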PSF 2/23/15 Page 18 of 37

The order of [\(^{11}\)C]CUMI-101 and [\(^{11}\)C]DASB administration may be reversed, or subjects may participate in only one scan (either [\(^{11}\)C]CUMI-101 or [\(^{11}\)C]DASB),.

In cases where the subject has a hemoglobin level less than 12 for males and less than 11 for females, we would forgo blood drawing for the [11C]DASB scan except for one sample to be taken at the 50 minute time point, as outlined in the simultaneous estimation (SIME) approach. Likewise, we would forego blood drawing for the [11C]CUMI-101 scan except for one sample at the 60 minute time point. We have recently confirmed that this provides an excellent estimate of the plasma parameters necessary for quantification and modeling of this radioligand. It involves drawing one 12 cc sample off the arterial line at the 50 min post-radioligand injection time point. Therefore, instead of 120 cc being drawn during the DASB scan, we would reduce the blood drawn to 12 cc.

In the case that the two injections are planned but cannot be done on the same day once the PET procedures have been started, subjects may be asked to return on a separate day in order to complete the scans. If the PET procedure has to be rescheduled and placement of another aline is required, subject consent will be sought.

After the acute treatment period, the patients who are on either lithium or lamotrigine will have a second PET scanning session that is identical to the first: up to 20 mCi or less of [11C]CUMI-101 and up to 20 mCi of [11C]DASB. Healthy volunteers will not have follow up scans.

Alternate Location and Tracer for PET Scans

Due to limited availability of PET scans at the Yale PET center, alternative arrangements will be made for subjects at Stony Brook Medicine. In cases where the subject cannot accommodate a trip to the Yale PET center or the Yale PET center cannot accommodate for enough scans due to decreased scan staff, PET/MRI scans may take place at the Siemens Biograph mMR-System located at the Ambulatory Imaging Center using [18F]MeFWAY. Similar to the [11C]CUMI-101 scans being performed at the Yale PET center, [18F]MeFWAY also has the capability to examine 5-HT_{1A} binding. Only bipolar and unipolar patients will be scanned at Stony Brook, when Yale is unable to accommodate the number of scans necessary. Healthy controls will continue to be scanned at Yale PET Center.

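### The SAP's pre/post analyses do not separate lithium from lamotrigine, so as written they do not answer drug-specific Aims 2-4

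*SAP*

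**What the plan says.** **Aims.** Protocol Section A sets the aims by drug: lithium on 5-HTT (Aim 2), lithium on 5-HT1A (Aim 3) and lamotrigine on both (Aim 4). Aims 2 and 4 also ask how binding change relates to antidepressant effect. Section D.1 states that lithium and lamotrigine are to be compared.

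**Who is rescanned.** Under PET Studies, "the patients who are on either lithium or lamotrigine will have a second PET scanning session that is identical to the first". Aim 4 expects about 50% of subjects to be ineligible for lithium. Treatment Choice gives lamotrigine to patients with prior lithium non-response or who refuse lithium. It also switches patients who lack sufficient HDRS improvement or cannot tolerate treatment.

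**Section E.** The paragraph opens "To assess the impact of lithium on the neuroreceptor measures" and gives power for a paired analysis, "Assuming 50% of the subjects complete the lithium treatment and repeat scans". Its pre/post model is written for non-remitters, "with ROI and condition (before/after) as fixed effects"; further covariates may be added when appropriate.

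**SAP.** Neither drug is named.
- Question 1: "Sample: HC, pre BPD, post BPD".
- Question 2: "Sample: pre/post BPD pairs".
- Questions 3-4: "pre BPD with pre HDRS-24 + >7-week HDRS-24".
- Listed terms: Group, Group by ROI, change in HDRS, change in HDRS by ROI, remission, and PET in the ROI.
- Covariates: age for DASB; for CUMI, "CUMI: age, sex, previous med status". The last of these is exposure before the study, not the study drug.

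**The concern.** The aims ask three separate questions about two drugs, and the SAP's post-treatment analyses give one answer for both together. A single post-treatment bipolar mean is an average of the lithium and lamotrigine effects, weighted by however many patients happened to be on each drug at rescan. It cannot show whether lithium raises 5-HTT, whether lithium lowers 5-HT1A, or whether lamotrigine does either. The protocol notes that there are no data on lamotrigine and 5-HTT, so it gives no basis for assuming that the two effects are equal.

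The change-response association in Question 2 has the same problem, with an added complication. Drug is not randomised, and for switched patients the drug may depend on the HDRS course that Question 2 uses as its outcome.

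**Working it through.** **1. Is there a drug term anywhere?** I checked each SAP sample, listed term and covariate given above; none is the study drug. Section E's two mixed models use ROI with remission status, and ROI with before/after condition. Neither names drug.

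**2. What does the pooled estimate measure?** With n_Li lithium pairs and n_LTG lamotrigine pairs,

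pooled change = (n_Li × lithium change + n_LTG × lamotrigine change) / (n_Li + n_LTG).

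Inputs: a lithium change of 20% (lower end of the 20-25% in Section E) and a lamotrigine change of 0% (assumed, 5-HTT only). The documents give no pair counts by drug, so the splits are assumptions.

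| Lithium + lamotrigine pairs | Calculation | Pooled change |
|---|---|---|
| 19 + 10 | 380/29 | 13.1% |
| 19 + 19 | 380/38 | 10.0% |
| 13 + 25 | 260/38 | 6.8% |

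The drug effects are the same in every row; only the mix changes. Conversely, at 19 + 19 a pooled 10% fits lithium 20% with lamotrigine 0%, and equally 10% on each.

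**3. The plan's own power figure.** Section E states 79% to 90% power for a 20-25% change. It gives no SD, alpha or sidedness, so this cannot be reproduced outright. I assume 19 pairs (50% of the 38 bipolar patients), a two-sided 0.05 paired t-test (noncentral t, 18 df), and an increase on the log scale, because Section E analyses log BP.
- 79% power needs a standardised change of 0.671: SD = ln(1.20)/0.671 = 0.1823/0.671 = 0.272.
- 90% power needs 0.787: SD = ln(1.25)/0.787 = 0.2231/0.787 = 0.284.
- A single SD of 0.278 gives 77% and 91%, each within 2 points of the stated figures.

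The stated power is therefore consistent with about 19 lithium-only pairs.

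**4. Precision after splitting (DASB, log scale).** Half-width of the 95% interval = t(0.975, n−1) × SD/√n, with SD 0.272 and 0.284.

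| Pairs | t | Half-width |
|---|---|---|
| 38 (pooled) | 2.026 | 0.089-0.093 |
| 19 (lithium) | 2.101 | 0.131-0.137 |
| 13 (lithium) | 2.179 | 0.164-0.171 |
| 10 (lithium) | 2.262 | 0.194-0.203 |

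The 38-pair row assumes no dropout and equal drug effects. If lithium raises binding by 20% and lamotrigine has no effect, the pooled SD becomes √(SD² + 0.25 × 0.1823²) = 0.287-0.298 and the half-width 0.094-0.098. These widths need not apply to CUMI, for which the protocol's toxicology section reports a test-retest CV below 10%.

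**5. Switching and rescan.** Treatment Choice places the repeat scans 6-10 weeks from the therapeutic or highest tolerable dose, and the switch for insufficient HDRS improvement at 6 weeks. For intolerant patients it says the rescan follows on lamotrigine. For non-responders it does not say whether the rescan comes before or after the switch. The SAP does not say which drug a switched patient's post scan represents.

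**The case against.** The strongest reply is that the documents taken together do not intend to pool. The aims are set by drug, Section D.1 says the drugs will be compared, and Section E's pre/post model stands in a paragraph that opens with the impact of lithium, so it may be meant as the lithium analysis. The SAP is headed as a proposed plan, has open question marks, and may supplement Section E. All of this stands. A reader might infer that the investigators chose to pool, or that no passage separates the drugs; the documents do not support either. What remains is narrower: a separation stated in the protocol is missing from the SAP, and Section E's model is written for non-remitters and names no drug.

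Three other stronger readings also fail.
- **Nineteen lithium pairs as a ceiling.** The 50% figure is a planning estimate from clinic experience, and Treatment Choice makes lithium the default.
- **The 0% lamotrigine scenario for 5-HT1A.** Aim 4 says lamotrigine, like lithium, alters that receptor, so the illustration is confined to 5-HTT.
- **Questions 3-4 as equally deficient.** No aim asks whether baseline PET predicts response to a particular drug, and predicting response to protocol treatment is a legitimate question. Moving their outcome to an early fixed time point would also have costs: the stated lamotrigine titration takes 4 weeks to reach its last step, and visits may be as infrequent as monthly.

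**Conclusion.** The point holds for Questions 1 and 2 and must be fixed. As written, their pre/post results are two-drug mixtures that answer none of Aims 2-4. This finding rests on the text and needs no assumed number. The size of the distortion cannot be known from the documents: under the assumed 5-HTT effects and drug splits, a 20% lithium change appears as anything from 13.1% down to 6.8%. There would be no distortion if the two drugs had the same effect. For Questions 3-4 the matter is a suggestion only.

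**What to change.** **Questions 1-2.**
- Replace the single post-treatment bipolar level with post-lithium and post-lamotrigine levels (drug by condition).
- Make the within-patient lithium contrast primary for Aims 2-3 and the lamotrigine contrast exploratory for Aim 4.
- Report the change-response association within each drug.
- Classify patients by the drug taken at the repeat scan, flag lamotrigine patients previously exposed to study lithium, and report the numbers switched before rescan, with reasons.
- State that the lithium-at-rescan group may be selected for response and tolerance, and that any between-drug comparison is non-randomised.

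**Protocol.** The Treatment Choice statements on switch and rescan for non-responders must be reconciled, so that the drug at rescan is defined.

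**Suggestion for Questions 3-4.** Include or stratify by study drug, and state from when the SAP's 7-week minimum is counted.

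**Cost.** SAP wording, a record of switches and analysis work; no new scans or visits. The price is precision: the DASB log-scale half-width is about 0.13-0.14 with 19 lithium pairs, 0.16-0.17 with 13 and about 0.20 with 10, against roughly 0.09-0.10 for 38 pooled pairs. The narrower pooled interval answers a question that no aim asks, and the lithium-only analysis is the one that Section E powers.
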